Results: Caregiver depressive symptoms and the child's asthma symptoms improved significantly (Table 1). Emergency Room (ER) and unscheduled visits decreased with substantial effect sizes, but did not reach statistical significance because of the small sample size. **Reduction in caregiver HRSD scores correlated strongly with change in peak expiratory flow ($r = -0.93, p = 0.002$), PASS (asthma symptoms) scores in the child ($r = 0.78$), as well as quality of life in the caregiver ($r = -0.85, p = 0.007$).**

Table 1. Caregiver Depressive Symptoms, Caregiver and Child Quality of Life, Child Asthma Symptoms, and Asthma-related Service Utilization Before and During Antidepressant Treatment

Assessment	HRSD (Caregiver)	QIDS-SR (Caregiver)	PASS (Child)	Asthma Related Hospitalizations (per month)	ER Visits (per month)	Unscheduled Clinic Visits (per month)
Baseline	20.9 ± 5.8	13.9 ± 3.9	19.4 ± 9.9	0.13 ± 0.06	0.30 ± 0.21	0.34 ± 0.39
Exit	15.5 ± 7.9	10.9 ± 4.9	13.3 ± 8.0	0.11 ± 0.17	0.16 ± 0.18	0.14 ± 0.18
Significance	p = 0.08	p = 0.03	p = 0.05	p = 0.76	p = 0.06	p = 0.07
Effect size (Cohen's d)	0.84	0.68	0.68	0.16	0.72	0.66

Significance: Findings from this pilot study suggest that antidepressant treatment was associated with improvement in caregiver depression as well as reduction in asthma symptoms and service utilization for the child. In addition, the study demonstrates a strong relationship between change in caregiver depressive symptoms and the child's asthma. These findings suggest that improvement in depressive symptoms in caregivers may be associated with improved outcomes related to the child's asthma.

3.3.a.iii. Pilot Study 3: Depressive Symptoms are Common in Children with Asthma, and They May Impact Asthma-related Service Utilization: This pilot study examined depressive symptoms in *children* with asthma, *not* their caregivers.²²

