Aim 2. Determine if improvement in depressive symptoms in caregivers of children with asthma predicts reduced unscheduled asthma-related service utilization. Separate analyses will be done for each event (ER visits, hospitalizations and unscheduled appointments). The dependent variable will be a count of the number of times the event occurred during the 52 week study period. This number will be converted to events per month to adjust for subjects who do not complete 52 weeks. The independent variables will be caregiver depressive symptoms as measured by HRSD along with site, baseline depressive symptoms, baseline asthma symptoms, and season of the year. Other baseline demographic and clinical variables (such as child's age) will be added if they improve the fit of the final model. Because the dependent variable is accumulated over the study period, caregiver HRSD will also be summarized over the study period for each subject by computing a seasonally adjusted slope of change over time during the 52 week study. All participants with two or more post-baseline HRSD measurements will be included in the analyses. Count data typically follow a Poisson distribution. Therefore, a generalized linear mixed model with Poisson link function will be used (SAS Proc GLIMMIX). Intercepts will be random effects. If an excessive number of subjects have zero events and the Poisson distribution is not appropriate (which often occurs with count data), then we will consider negative binomial models, zero-inflated Poisson models, and hurdle models. At times caregiver depression may get worse, despite treatment. Therefore, we will examine whether increases in caregiver depressive symptom severity predicts worse child asthma outcomes. The same model used above will be used here except that an indicator variable will be added to indicate if caregiver HRSD scores worsened or stayed the same during the study (zero or positive slope) versus improved (negative slope). The addition of this indicator variable will allow the relationship between change in HRSD and utilization events to differ for those who worsen or stay the same versus those who improve. This aim will be tested by the significance of this additional indicator variable. The primary analysis for this aim will use HRSD scores and ER visits (sensitive to the intervention in Pilot Study #2 and an important clinical outcome). However, similar analysis will be conducted using the QIDS-SR and STAI in place of the HRSD, and using unscheduled clinic visits and hospitalizations.

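### Aim 2's test of worsening caregiver depression measures only a jump in event rate at zero HRSD slope, so a null result cannot show that worsening is harmless

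*Combined protocol and SAP*

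**What the plan says.** Section 3.4, Aim 2, models each type of event with a Poisson mixed model. The main predictor is one HRSD value per caregiver, obtained by "computing a seasonally adjusted slope of change over time during the 52 week study". Worsened caregivers belong to that main analysis: "All participants with two or more post-baseline HRSD measurements will be included in the analyses".

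The section then raises a further question: "we will examine whether increases in caregiver depressive symptom severity predicts worse child asthma outcomes". The model for it is described as follows: "The same model used above will be used here except that an indicator variable will be added". The indicator separates caregivers whose HRSD slope is zero or positive from those whose slope is negative. Its stated purpose is: "The addition of this indicator variable will allow the relationship between change in HRSD and utilization events to differ" between those two groups. The decision rule is: "This aim will be tested by the significance of this additional indicator variable".

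No product or piecewise term is named, no slope among worsened caregivers is to be estimated, and no other test is given for this question.

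**The concern.** The question, the property claimed for the model and the test do not match. Whether worsening predicts more events concerns the slope above zero. Whether the relationship differs between groups concerns a change of slope, a jump, or both. The indicator's coefficient beside a shared slope measures only the jump.

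A null indicator is therefore what one should expect when worsening and improvement act along a single line. With no other test assigned to the question, that null invites the reading that worsening does no harm, next to a main Aim 2 result that says the opposite. The plan calls for similar analyses with QIDS-SR, STAI, clinic visits and hospitalizations; any repeat of the worsening test there has the same defect.

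**Working it through.** **The plan's own figure.** Section 3.4 (Power) gives a detectable f² = 0.10 for Aim 2 with N = 175, 10 predictors and 80% power. A 10-df F test with error df 175 − 10 − 1 = 164, noncentrality f²·N and alpha 0.05 (assumed) gives f² = 0.098 at 80% power, and 81.0% power at f² = 0.10. The figure reproduces, but it is for a joint 10-df test and says nothing specific about the indicator.

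**Algebra.** Let s be the HRSD slope and I = 1 if s ≥ 0. The planned model is

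log rate = b0 + b1·s + b2·I + covariates.

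- Improved caregivers: b0 + b1·s
- Worsened or unchanged caregivers: (b0 + b2) + b1·s

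The slope is b1 in both groups and the gap is b2 at every s. If the truth is b0 + β·s throughout, then b1 = β and b2 = 0. With β = 0.35 per SD of slope, each SD of worsening multiplies the rate by exp(0.35) = 1.42, yet b2 is still zero. Covariates, random intercepts and the negative binomial alternative do not change this.

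With a product term b3·s·I, the slope among the worsened is b1 + b3. The coefficient b2 is still only the jump at s = 0 (slope uncentred), so naming the product term while still testing b2 would not repair the rule.

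**Simulation inputs.**
- From the documents: n = 175 (Power); ER visits 0.16 per month at pilot exit, × 12 = 1.9 per year, and 0.30 at pilot baseline, × 12 = 3.6 per year (section 3.3.a.ii, Table 1).
- Assumed: s ~ N(m, 1) with m = −0.8 (21% worsening), varied to −1.28 (10%) and −0.39 (35%); negative binomial dispersion 0.5, varied from 0.25 to 1.0; effects per SD of slope; no covariates; two-sided 5% Wald tests.
- Base case 1,000 trials per scenario; inputs varied one at a time, 500 trials each.

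Percent significant, base case (range):

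| Truth | Planned indicator | Interaction | 2-df joint test |
|---|---|---|---|
| Common slope 0.35 | 7 (4-7) | 5 (4-6) | about 4 |
| Common slope 0.20 | 4 (4-7) | not tabulated | not tabulated |
| Effect only in worsened, 0.8 | 21 (10-27) | 63 (27-80) | 62 (35-77) |
| Slopes 0.25 below, 0.9 above zero | 12 (5-20) | 51 (24-65) | 48 (26-57) |
| Step of 0.5 at zero | 45 (30-59) | 5 (4-7) | 37 (24-50) |

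The joint-test figure for the common slope comes from a smaller run of 300 trials. With no effect at all, every test was significant in 4-6% of trials.

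Under the common slopes, the existing overall slope test was significant in 99% (94-100) at 0.35 and 72% (56-85) at 0.20. The slope among the worsened, b1 + b3, was significant in 23% (13-41) and 10% (5-16).

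**Second simulation.** Poisson counts, effects per HRSD point, 13-33% worsening:
- Same effect on both sides (0.05 per point): indicator 4-6%, overall slope 98-100%.
- Only worsening matters (0.08 per point): indicator 8-39%, product term 30-100%.
- Only improvement matters: indicator 7-13%, with a negative average coefficient.
- Jump of 0.5 at zero: indicator 74-99%.

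The powers are higher without overdispersion; the pattern is the same.

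**The case against.** The plan never says that a non-significant indicator will be read as no effect. If the question is only whether the relationship differs between groups, a null under a common slope is the correct answer. The main Aim 2 test also covers worsened caregivers and would usually show an association: in a base-case run of 300 trials it was significant in about 73% (effect only in worsened), 100% (slopes 0.25 and 0.9) and 55% (step). Under a common slope the added tests gain nothing in power: the joint test stays near 4%, and the worsened-range slope reaches only 23%. Most simulation inputs are assumed, and the ER rate comes from a pilot of eight caregivers.

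Much of this stands. It limits the harm to one supplementary question in a secondary aim, and it means the percentages show a pattern rather than predict power. It does not rescue the rule. The opening sentence asks whether worsening predicts worse outcomes, and the indicator is the only test assigned to that. On the narrower reading the indicator is still a weak test of a slope difference (21% against 63%), and the statement that it lets the relationship differ is true only of a level shift. The main slope test cannot say whether an association lies in the worsened range.

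**Conclusion.** The concern holds. As specified, the indicator tests a level shift at zero slope and nothing more by design. That follows from the model and needs no assumed inputs. Under a common slope the rule rejects at about its type I error rate (4-7%) while the overall slope is detected in 94-100% of trials at 0.35 per SD. Where only worsening matters, the indicator has about a third of the interaction's power (21/63 = 0.33). It is the better test for a pure step (45% against 37% for the joint test).

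The sizes depend on the assumed slope distribution, share worsening, dispersion and effects, and on leaving out covariates and error in the estimated slopes. The primary analysis, the sample size and the main Aim 2 test are not affected. The wording suggests that an interaction may have been intended, but none is specified. The text should be corrected before analysis.

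**What to change.** In section 3.4, Aim 2:

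1. Keep the slope and the indicator, and add a slope-by-indicator term.
2. Describe the indicator's coefficient as a level shift at zero slope.
3. Test whether the relationship differs with the 2-df joint test of indicator and interaction, and report both coefficients.
4. Answer whether worsening predicts worse outcomes with the overall slope, together with the estimated slope among worsened caregivers (b1 + b3) and its confidence interval. The interaction alone will not do, because it too is zero under a common slope.
5. State in advance that a null result in the worsened range will be reported as imprecise, not as absence of effect.

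This takes two or three sentences and one model term, with no new data. The joint test gives up some power for a pure step (45% to 37%) and gains little if only 10% worsen (23% to 35% for an effect confined to the worsened). The worsened-range slope will be imprecise. In the base case with common slope 0.35, the median 95% half-width is 0.63 log units: rate ratio exp(0.35) = 1.42, interval exp(0.35 − 0.63) = 0.76 to exp(0.35 + 0.63) = 2.66. The half-width rises to about 1.1 if 10% worsen.

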Power: No data exist on which to base a power analysis. However, the hypothesis tests used here involve testing regression coefficients. To obtain an approximate idea of the power of our tests, we can refer to the test of a regression coefficient that can be detected with 80% power given a sample of 175. If we conservatively assume 10 predictors for the Primary Aim and Secondary Aim 2, then an effect size of $f^2 = 0.10$ could be detected. This effect size is classified as small ($f^2 = 0.02$) to medium ($f^2 = 0.15$) according to Cohen.⁶⁹ In the full model for Secondary Aims 1, 2 and 3 there are 13 measurement occasions and approximately 200 paths; however, the hypotheses to be tested involve the 78 paths between each visit and each later visit. Given this number of predictors to be tested, an effect size of 0.31 could be detected with 80% power. This effect size is classified as medium ($f^2 = 0.15$) to large ($f^2 = 0.35$) according to Cohen.⁶⁹

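### The only sentence naming a deciding test for Aim 2 points to the worsened/improved indicator, which tests for a jump at zero HRSD slope and not whether improvement predicts fewer ER visits

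*Combined protocol and SAP*

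**What the plan says.** All of this stands in the Combined protocol and SAP, section 3.4, under Aim 2.

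- **Objective:** "Determine if improvement in depressive symptoms in caregivers of children with asthma predicts reduced unscheduled asthma-related service utilization".
- **Main model:** a Poisson generalized linear mixed model. HRSD is summarised per caregiver by "computing a seasonally adjusted slope of change over time during the 52 week study", with site, baseline depressive symptoms, baseline asthma symptoms and season as further predictors.
- **Sub-question:** after noting that some caregivers may get worse, the text continues "Therefore, we will examine whether increases in caregiver depressive symptom severity predicts worse child asthma outcomes". The main model is kept with one addition, worded as follows: "an indicator variable will be added to indicate if caregiver HRSD scores worsened or stayed the same during the study (zero or positive slope"). Caregivers with a negative slope count as improved. This is said to let the relation between HRSD change and utilization differ between the two groups.
- **Deciding sentence:** "This aim will be tested by the significance of this additional indicator variable".
- **Next sentence:** "The primary analysis for this aim will use HRSD scores and ER visits".

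The Power paragraph says only that the hypothesis tests involve regression coefficients. It refers to "a regression coefficient that can be detected with 80% power given a sample of 175" and does not say which coefficient. No alpha or sidedness is given for Aim 2.

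**The concern.** The coefficient that answers Aim 2 is that of the HRSD slope in the main model. The plan specifies that model but never says that its slope coefficient decides the aim. The one sentence that assigns a test assigns it to a term in a second model, where the slope is already present. An analyst who follows the text could therefore report Aim 2 as not shown in data where improvement clearly goes with fewer ER visits. An analyst who follows the evident purpose would report the opposite from the same data. The plan should not leave that choice until after the data are seen.

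There is a second problem in the same lines. Even for the question about worsening caregivers, an indicator on its own does not do what the text says it does.

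**Working it through.** **1. The plan's own figure.** The Power paragraph gives a detectable f² of 0.10 at 80% power for N = 175 and 10 predictors. For a 10-df F test with noncentrality f² × N = 0.10 × 175 = 17.5 on 10 and 164 df, at alpha 0.05, power is 81.0%; 80% is reached at f² = 0.098. The figure is reproduced, but as an omnibus test of all ten predictors. A single coefficient in the same model would reach 80% power at f² = 0.045. The paragraph therefore does not show which coefficient decides Aim 2.

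**2. What the indicator tests.** Let s be the HRSD slope and I = 1 when s ≥ 0. The second model is

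log(rate) = a + b·s + c·I + covariates.

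- Improving caregivers: a + b·s.
- Worsening or unchanged caregivers: (a + c) + b·s.

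The coefficient b is the same in both groups. So c is a jump in the log rate at s = 0, and nothing in this model lets the relation with HRSD change differ by group. That needs a further term d·(s·I). If the log rate is linear in s, which is what the main model assumes, then c = 0 for every b, and the test of c rejects at its alpha level.

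**3. Inputs for the size.** These are assumptions unless a source is given.

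- N = 175 (Power paragraph); 196 also tried.
- ER visits: 0.16 a month at pilot exit × 12 = 1.92 a year; 0.30 a month at pilot baseline × 12 = 3.6 a year (Table 1; eight caregivers).
- Share with zero or positive slope: 20% if the mean slope is −0.84 SD (borrowed from the pilot HRSD effect size); range 10% to 31% for −1.3 to −0.5 SD.
- Two-sided alpha 0.05.

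**4. Log-linear truth, Poisson counts** (4,000 simulated trials per row, N = 175, 1.92 visits a year; site, baseline depression and baseline asthma as covariates):

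| Rate ratio per SD of slope | Slope test, main model | Indicator test |
|---|---|---|
| 1.00 | 5.3% | 5.5% |
| 1.11 | 44% | 4.2% |
| 1.22 | 95% | 5.0% |
| 1.49 | about 100% | 4.8% |
| 2.01 | about 100% | 5.2% |

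At 3.6 visits a year the indicator rejects in 4.6% to 5.6%. It stays at about 4% to 6% with 10% to 31% worsening, N = 175 or 196, overdispersed counts, and measurement error in the slope.

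**5. Log-linear truth, negative binomial counts** (1,000 trials per row; 2.0 visits a year; slope mean −0.8 and SD 0.8 points a month, so 16% at or above zero; no covariates):

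| Dispersion | Rate ratio per point a month | Slope test | Indicator test |
|---|---|---|---|
| 1.0 | exp(0.2) | 41% | 5% |
| 1.0 | exp(0.3) | 72% | 7% |
| 1.0 | exp(0.4) | 92% | 5% |
| 0.5 | exp(0.3) | 86% | 4% |
| 0.5 | exp(0.4) | 98% | 5% |

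With SD 0.8, exp(0.2) to exp(0.4) per point a month is exp(0.16) to exp(0.32), or 1.17 to 1.38, per SD.

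**6. Other shapes.** Power of the indicator when the log rate is not linear in the slope:

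| True shape | Size 0.2 | Size 0.4 | Size 0.7 |
|---|---|---|---|
| Effect confined to improvers (log rate ratio per SD) | 8% | 12% | 24% |
| Rate linear on the natural scale (relative change per SD) | 7% | 19% | 46% |
| Added step at zero slope (log rate ratio) | 20–21% | 64–65% | 98% |

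The indicator gains power as the curve departs from log-linearity at zero. That is a different question from whether improvement predicts fewer visits.

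**The case against.** **The sentence may belong to the sub-question.** It closes a block that opens with caregivers who worsen, and the model there is described as the earlier one with one addition. The Missing Data and Power paragraphs also speak of a Primary Aim and numbered Secondary Aims that do not match Aims 1 to 4, so the wording may be left over from a scheme in which worsening was its own aim. This is plausible, and the documents cannot settle it. But on that reading Aim 2 has no stated deciding test, and the following sentence still uses the same phrase for the whole aim.

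**A reader might infer that Aim 2 has about 5% power however strong the effect.** The documents do not support that. It needs a log-linear relation; smoothness alone is not enough, since a rate linear on the natural scale gives 7% to 46%.

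**A reader might infer that the false-positive rate for Aim 2 roughly doubles**, to 9% to 10% with two tests. That needs a rule that either test may be claimed, and the plan has none.

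**The slope test is not sure to succeed.** This stands. At exp(0.2) and dispersion 1.0 it has 41% power. In a check that added baseline depression, assumed to correlate 0.5 with the slope, power at exp(0.2), exp(0.3) and exp(0.4) fell from 42%, 75% and 91% to 32%, 58% and 84%.

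**The inputs are soft.** This stands too. The pilot fall of 20.9 − 15.5 = 5.4 points over 6 months is 0.9 a month, against 0.8 in the negative binomial runs, and the slope SD is not in the documents.

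**Conclusion.** The point holds as an error in the stated decision rule, not as proof that the sponsor means to decide Aim 2 on the indicator. Taken literally, the rule uses a coefficient that does not measure what Aim 2 asks; taken narrowly, the aim has no named test. Under the planned log-linear model the indicator rejects at about the alpha level whatever the effect, against about 40% to 98% for the slope in the negative binomial settings above. Those figures rest on two-sided 0.05, an assumed slope distribution and event rates from a pilot of eight.

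The point about the missing interaction needs none of these assumptions, because it follows from the form of the model. It applies on either reading of the sentence.

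**What to change.** In section 3.4, Aim 2:

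1. State that Aim 2 is decided by the HRSD-slope coefficient in the ER-visit model without the indicator, and give alpha and sidedness (for example, two-sided 0.05).
2. Reword the deciding sentence so that it refers only to the question about worsening caregivers, and label that a secondary analysis that does not decide Aim 2.
3. For that question, fit the indicator together with a slope-by-indicator interaction.

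The cost is a few sentences, with no new data and no loss of power for the aim's own question. The downside is that a finding specific to worsening caregivers becomes secondary. The interaction will also have low power: at 10% to 31% of 175, only about 18 to 54 caregivers would have a zero or positive slope.
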